14.3 Adverse Event, Device Deficiency, Adverse Device Effect, reporting

The Investigator will record any AEs, Device Deficiency and ADEs occurring during the study. He/She will also co-operate with the Sponsor in connection with the reporting of any "reportable event" to the Competent Authority and to the Independent EC, if applicable.

All AEs regardless of severity occurring between recruitment and completion of the study by a subject must be recorded on the AE form provided with the CRF.

If there is a significant worsening of a medical condition that was present before starting the study, this should be considered as a new AE and a complete evaluation recorded. Signs and symptoms considered as lack of efficacy and occurring during the study will not be recorded on the AEs Section of the CRF except on the condition that, in the Investigator's opinion, these signs and symptoms are caused by any reason different from lack of efficacy of the study product or meet the definition of serious AE.

In the event of a SAE (including a reportable event) the Investigator has to:

- Complete the relevant CRF pages and a reporting form with the available initial information.
- Immediately inform the Sponsor or the CRO by telephone,

CONFIDENTIAL Page 39 of 51

 Fax the completed report form to the contact person at the Sponsor or the CRO as soon as possible but no later than 3 calendar days after the investigation site study personnel's awareness of the event.

Reporting contacts are on page 4 of this Clinical Investigation Plan.

The Investigator is responsible for ensuring the follow-up of any subject who experiences a serious adverse event (including any reportable event) during the study. The investigator must re-examine the subject at regular intervals until the symptoms have completely disappeared or stabilized.

The Sponsor or its delegate will be responsible for reporting the SAE/SADE/Serious Incident to the appropriate Authorities and EC, according to the local regulations.

15. Vulnerable Population

No vulnerable population will be included in this clinical investigation.

16. Suspension or Premature Termination of the Clinical Investigation

Unless premature interruption occurs, the end of the study will be the closure visit at clinical site.

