5.3 Tolerability and Safety Objectives and Endpoints

To evaluate the local safety at injection site (pain, erythema, edema, bruising) and the systemic safety of the treatment with Foliage Hydrofil.

Safety endpoints are:

- the number, typology, severity of local and systemic adverse events. Particular attention will be paid to local adverse events like pain, erythema, edema, bruising.

6. Design of the Clinical Investigation

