14.1 Definitions

Adverse Event (AE)

Any untoward medical occurrence, unintended disease or injury or any untoward clinical signs, including an abnormal laboratory finding, in subjects, users or other persons, in the context of a clinical investigation, whether or not related to the investigational device.

Adverse Device Effect (ADE)

Any untoward and unintended response to a medical device. This includes any event resulting from insufficiencies or inadequacies in the instructions for use or the deployment of the device and any event that is a result of a user error.

Device Deficiency

Any inadequacy in the identity, quality, durability, reliability, safety or performance of an investigational device, including malfunction, use errors or inadequacy in information supplied by the manufacturer.

Serious Adverse Event (SAE)

Any adverse event that led to any of the following:

- a) death,
- b) serious deterioration in the health of the subject, that resulted in any of the following:
 - i. life-threatening illness or injury,
 - ii. permanent impairment of a body structure or a body function,
 - iii. hospitalisation or prolongation of patient hospitalisation,
 - iv. medical or surgical intervention to prevent life-threatening illness or injury or permanent impairment to a body structure or a body function,
 - v. chronic disease
- c) foetal distress, foetal death or a congenital physical or mental impairment or birth defect.

CONFIDENTIAL Page 37 of 51

Serious Adverse Device Effect (SADE)

Adverse device effect that has resulted in any of the consequences characteristic of a serious adverse event or that might have led to any of these consequences if suitable action had not been taken or intervention had not been made or if circumstances had been less opportune.

Unanticipated Serious Adverse Device Effect (USADE)

Serious adverse device effect that by its nature, incidence, severity or outcome has not been identified in the risk analysis report.

Incident

Any malfunction or deterioration in the characteristics and/or performance of a device, as well as any lack of labelling or instructions for use which, directly or indirectly, may cause or have caused death or serious deterioration in the health of the patient or of a user or of other persons.

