#### **5.3** Safety Endpoints

Safety endpoints are the number, typology, severity of local and systemic adverse events. Particular attention will be paid to local adverse events like pain, erythema, edema, bruising.

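### Protocol 14.3 lets non-serious worsening of the treated skin stay out of the adverse event tables when the Investigator attributes it to lack of efficacy

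*Protocol*

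**What the plan says.** Protocol 14.1 defines an adverse event broadly, as "Any untoward medical occurrence, unintended disease or injury or any untoward clinical signs", regardless of any relation to the device. Protocol 14.3 then sets the recording rules in three steps.

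- The general rule: "All AEs regardless of severity occurring between recruitment and completion of the study by a subject must be recorded on the AE form".
- A rule for existing conditions: if there is a "significant worsening of a medical condition that was present before starting the study, this should be considered as a new AE".
- An exemption: "Signs and symptoms considered as lack of efficacy and occurring during the study will not be recorded on the AEs Section of the CRF". It has two exceptions, "except on the condition that, in the Investigator's opinion, these signs and symptoms are caused by any reason different from lack of efficacy" of the product, "or meet the definition of serious AE".

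The safety endpoint in Protocol 5.3 is "the number, typology, severity of local and systemic adverse events", and SAP 5.3 repeats it. Both single out pain, erythema, edema and bruising as examples of local events. SAP 14.3 lists two safety tables: 3.1, an analysis of adverse events, and 3.2, a display of them by system organ class and preferred term.

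**The concern.** Under 14.1 the cause of an untoward sign has no bearing on whether it is an adverse event; cause belongs in the causality classification of 14.2. The exemption in 14.3 turns attributed cause into the test for entry. It gives no criterion for telling a face that has not improved from one that has become worse.

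This matters more here than in most studies because performance and local safety concern the same tissue. Hydration, texture, tone, fine lines and wrinkles are performance items, and they are also features of the injected skin. The Investigator who scores skin quality and GAIS also decides whether a sign counts as lack of efficacy, with no blinding and no control arm. What is at stake is the completeness of the local adverse event count. The exemption can take events out of that count and cannot put any in.

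**Working it through.** **1. The rules set against each other.** Take a subject whose treated skin is visibly rougher at Visit 3 than at Visit 1, with nothing serious about it.

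| Rule | Result |
|---|---|
| 14.1 definition | Adverse event, whatever the cause |
| 14.3, general rule | Must be recorded |
| 14.3, significant worsening | New adverse event, if aged facial skin counts as a medical condition and the worsening is significant |
| 14.3, exemption | Not recorded, if the Investigator considers it lack of efficacy |

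Visible skin aging is inclusion criterion 3, but neither document says whether it is a medical condition for the third rule. The third and fourth rules can therefore give opposite answers for the same finding.

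**2. What an omission requires.** All three of these must hold: the sign is non-serious; it is not treated as significant worsening of a pre-existing condition; and the Investigator attributes it to lack of efficacy and not to the injection, the product or anything else.

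**3. Whether another route leads into the safety tables.** The flow chart (Protocol Table 1) has a row for adverse event collection and none for a separate local tolerability assessment. Protocol 7.3.6 promises a summary of local tolerability. SAP 12.2 says only that it will be considered, and SAP 14.3 lists no table for it beyond 3.1 and 3.2. A sign kept off the adverse event section does not reach either table.

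**4. Where the worsening would still be seen.** GAIS grade 1 and PAIS grade 1 record worsening at Visits 2, 3 and 4. The texture, tone, fine-line and wrinkle scales and the corneometer reading are taken at the same visits. SAP 11.4.2 summarises the scales by number and percentage, and Listings 5.1 to 5.4 give individual values. These records carry no CTCAE grade, causality or MedDRA term. Tables 2.2.4 to 2.2.6 are titled by improvement, and no SAP rule carries a grade 1 rating into the safety evaluation.

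**5. Size.** The plan states no figure to reproduce and no expected rate of worsening. The illustration below assumes a safety set equal to the planned 24 subjects (Protocol 7.1), k subjects whose only adverse event is omitted, and no adverse event in anyone else. Change in subject-level incidence = k/24. Exact 95% limits (Clopper-Pearson): lower = 2.5% quantile of Beta(k, 25 − k), zero when k = 0; upper = 97.5% quantile of Beta(k + 1, 24 − k).

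| k | True proportion (95% CI) | Reported |
|---|---|---|
| 1 | 1/24 = 4.2% (0.1 to 21.1) | 0/24 (0 to 14.2) |
| 2 | 2/24 = 8.3% (1.0 to 27.0) | 0/24 (0 to 14.2) |
| 3 | 3/24 = 12.5% (2.7 to 32.4) | 0/24 (0 to 14.2) |

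The mock of Table 3.1 (SAP 14.4.4) asks whether any adverse event occurred. If the affected subject already has another recorded event, the overall incidence changes by 0; only the event count and the relevant preferred-term row lose an entry.

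**6. Why a remedy needs a threshold.** Under the plan's own assumption for the Day 98 corneometer change (mean 7.5, SD 8) and normality, P(change < 0) = Φ(−7.5/8) = Φ(−0.94) ≈ 17%, and 24 × 0.17 ≈ 4 subjects. If every reading below baseline counted as an adverse event, a device performing exactly as planned would produce about four.

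**The case against.** The clause is narrower than it first looks. Anything serious and anything the Investigator ascribes to another cause must be recorded, so rough or dry skin thought to result from the injection goes on the form. Worsening that is seen as significant may be caught by the preceding sentence. The named local reactions are described in Protocol section 4 as side effects of treatment, and nothing in the plan suggests that they could be filed as lack of efficacy. Deterioration is also not lost: it is scored, photographed, examined and listed. All of this stands, and it limits the point. It does not resolve the conflict between the two sentences in 14.3, and it does not bring an exempted sign into Tables 3.1 or 3.2.

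Three stronger readings are tempting, and the documents do not support them.

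- A reader might infer that the whole local safety endpoint is unreliable. The exposure is confined to non-serious worsening of skin quality.
- A reader might infer that every omission costs 4.2 percentage points. That holds only for a subject with no other recorded event. After up to three injection sessions, for which the protocol expects mainly pain, erythema, edema and bruising, many subjects may already be counted.
- A reader might assume worsening rates of 2%, 5% or 10% and compute 1 − (1 − p)^24 = 38%, 71% or 92%. Those are the chances that at least one subject worsens at an assumed rate. The chance of an omission also needs the probability that the Investigator applies the label, and the documents give neither.

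**Conclusion.** The point holds in a limited form. The exemption in 14.3 conflicts with the definition in 14.1 and with the sentence before it, and it lets non-serious worsening of the treated skin, attributed to lack of efficacy, be absent from the adverse event tables. The direction is known: recorded events can only be too few. The size is not known. Per affected subject, the effect on overall incidence is 0 if another event is recorded and 4.2 percentage points if none is, assuming 24 subjects in the safety set. The conclusion also assumes that the Investigator would use the exemption for worsening as well as for lack of improvement; the wording permits this but does not require it. The primary analysis, serious events and the four named local reactions are untouched. The change is worth making because it uses data already collected.

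**What to change.** **Protocol 14.3.** Reconcile the two sentences. State that absence of improvement is not an adverse event. State that clinically apparent worsening of the treated area compared with Visit 1 is entered on the adverse event form, with the Investigator's attribution given in the causality field and not used to decide entry. Add that a lower corneometer reading or a scale rating is not by itself an adverse event.

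**SAP 12.2.** Before database lock, query each GAIS or PAIS grade 1 record that has no matching adverse event, so that the Investigator either enters the sign behind it or confirms that there was none. Report the cross-tabulation of grade 1 ratings against recorded adverse events beside Table 3.1. The SAP already describes recruitment and treatment in the past tense, so this step may be the only one that can still affect the data. It works through the query process in Protocol section 8.

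**Cost.** A short change to 14.3, one reconciliation check and one small table, with no new visit or assessment. The downside is a few more queries and adverse event forms, and possibly a slightly less favourable adverse event rate.

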16.1 Study Discontinuation

Subjects may be discontinued at any time from the study for any of the following reasons:

- An AE occurs that, in the opinion of the Investigator, makes it unsafe for the subject to continue in the study
- Lack of compliance of the subject to the study treatment or assessments
- The subject needs to use a medication/treatment not allowed
- The subject is lost to follow-up
- > The subject dies
- The subject withdraws consent

CONFIDENTIAL Page 40 of 51

- The Investigator, for any reason, terminates the entire study, or terminates the study for that subject or the attending physician requests that the subject be withdrawn for any medical reason
- The Sponsor or the Regulatory Authority or the Ethics Committee, for any reason, terminates the entire study or terminates the study for this site or for a particular subject.

If a subject is discontinued from the study, the Investigator will, as far as possible, complete the end of study visit (Visit 4) e-CRF fields. The Investigator should try to ascertain the reason(s) for withdrawal, while fully respecting the subject's rights.

16.2 Study Interruption

The Sponsor may consider study closure at the clinical site if the following occurs:

- serious and/or persistent non-compliance with the Clinical Investigation Plan
- inadequate collaboration of site personnel with CRO/Sponsor
- > administrative reasons
- non-compliance with GCP, SOPs or regulatory requirements
- > lack of confidentiality and/or non-compliance with the contract spread with the Sponsor.

17. Publication Policy

All information obtained as a result of the study will be regarded as confidential.

The results of the clinical study will be documented in an integrated clinical study report according to UNI EN ISO 14155.

The Sponsor and the Investigator agree that no publications presenting or discussing data and/or results from this clinical study sponsored by Phitogen Holding S.p.A. will take place until the participating center has completed the study, the data have been interpreted, and the final report has been issued.

As a rule, the Sponsor is free to use the data collected in the sponsored study for world-wide scientific product documentation, and for publication.

In general, the Sponsor has no objections if the Investigators publish the results of the study. However, the Investigator is requested to provide the Sponsor with a copy of the manuscript for review before submitting it to the publisher with a cover letter informing the Sponsor about the intention to publish the study results. When permission for

CONFIDENTIAL Page **41** of **51**

64th WMA General Assembly, Fortaleza, Brazil, October 2013

Preamble

1. The World Medical Association (WMA) has developed the Declaration of Helsinki as a statement of ethical principles for medical research involving human subjects, including research on identifiable human material and data.

The Declaration is intended to be read as a whole and each of its constituent paragraphs should be applied with consideration of all other relevant paragraphs.

2. Consistent with the mandate of the WMA, the Declaration is addressed primarily to physicians. The WMA encourages others who are involved in medical research involving human subjects to adopt these principles.

General Principles

- 3. The Declaration of Geneva of the WMA binds the physician with the words, "The health of my patient will be my first consideration," and the International Code of Medical Ethics declares that, "A physician shall act in the patient's best interest when providing medical care."
- 4. It is the duty of the physician to promote and safeguard the health, well-being and rights of patients, including those who are involved in medical research. The physician's knowledge and conscience are dedicated to the fulfilment of this duty.
- 5. Medical progress is based on research that ultimately must include studies involving human subjects.

CONFIDENTIAL Page 45 of 51

- 6. The primary purpose of medical research involving human subjects is to understand the causes, development and effects of diseases and improve preventive, diagnostic and therapeutic interventions (methods, procedures and treatments). Even the best proven interventions must be evaluated continually through research for their safety, effectiveness, efficiency, accessibility and quality.
- 7. Medical research is subject to ethical standards that promote and ensure respect for all human subjects and protect their health and rights.
- 8. While the primary purpose of medical research is to generate new knowledge, this goal can never take precedence over the rights and interests of individual research subjects.
- 9. It is the duty of physicians who are involved in medical research to protect the life, health, dignity, integrity, right to self-determination, privacy, and confidentiality of personal information of research subjects. The responsibility for the protection of research subjects must always rest with the physician or other health care professionals and never with the research subjects, even though they have given consent.
- 10. Physicians must consider the ethical, legal and regulatory norms and standards for research involving human subjects in their own countries as well as applicable international norms and standards. No national or international ethical, legal or regulatory requirement should reduce or eliminate any of the protections for research subjects set forth in this Declaration.
- 11. Medical research should be conducted in a manner that minimises possible harm to the environment.
- 12. Medical research involving human subjects must be conducted only by individuals with the appropriate ethics and scientific education, training and qualifications. Research on patients or healthy volunteers requires the supervision of a competent and appropriately qualified physician or other health care professional.
- 13. Groups that are underrepresented in medical research should be provided appropriate access to participation in research.
- 14. Physicians who combine medical research with medical care should involve their patients in research only to the extent that this is justified by its potential preventive, diagnostic or therapeutic value and if the physician has good reason to believe that participation in the research study will not adversely affect the health of the patients who serve as research subjects.
- 15. Appropriate compensation and treatment for subjects who are harmed as a result of participating in research must be ensured.

Risks, Burdens and Benefits

CONFIDENTIAL Page 46 of 51

16. In medical practice and in medical research, most interventions involve risks and burdens.

Medical research involving human subjects may only be conducted if the importance of the objective outweighs the risks and burdens to the research subjects.

17. All medical research involving human subjects must be preceded by careful assessment of predictable risks and burdens to the individuals and groups involved in the research in comparison with foreseeable benefits to them and to other individuals or groups affected by the condition under investigation.

Measures to minimise the risks must be implemented. The risks must be continuously monitored, assessed and documented by the researcher.

18. Physicians may not be involved in a research study involving human subjects unless they are confident that the risks have been adequately assessed and can be satisfactorily managed.

When the risks are found to outweigh the potential benefits or when there is conclusive proof of definitive outcomes, physicians must assess whether to continue, modify or immediately stop the study.

Vulnerable Groups and Individuals

19. Some groups and individuals are particularly vulnerable and may have an increased likelihood of being wronged or of incurring additional harm.

All vulnerable groups and individuals should receive specifically considered protection.

20. Medical research with a vulnerable group is only justified if the research is responsive to the health needs or priorities of this group and the research cannot be carried out in a non-vulnerable group. In addition, this group should stand to benefit from the knowledge, practices or interventions that result from the research.

Scientific Requirements and Research Protocols

- 21. Medical research involving human subjects must conform to generally accepted scientific principles, be based on a thorough knowledge of the scientific literature, other relevant sources of information, and adequate laboratory and, as appropriate, animal experimentation. The welfare of animals used for research must be respected.
- 22. The design and performance of each research study involving human subjects must be clearly described and justified in a research protocol.

The protocol should contain a statement of the ethical considerations involved and should indicate how the principles in this Declaration have been addressed. The protocol should include information

CONFIDENTIAL Page 47 of 51

regarding funding, sponsors, institutional affiliations, potential conflicts of interest, incentives for subjects and information regarding provisions for treating and/or compensating subjects who are harmed as a consequence of participation in the research study.

In clinical trials, the protocol must also describe appropriate arrangements for post-trial provisions.

Research Ethics Committees

23. The research protocol must be submitted for consideration, comment, guidance and approval to the concerned research ethics committee before the study begins. This committee must be transparent in its functioning, must be independent of the researcher, the sponsor and any other undue influence and must be duly qualified. It must take into consideration the laws and regulations of the country or countries in which the research is to be performed as well as applicable international norms and standards but these must not be allowed to reduce or eliminate any of the protections for research subjects set forth in this Declaration.

The committee must have the right to monitor ongoing studies. The researcher must provide monitoring information to the committee, especially information about any serious adverse events. No amendment to the protocol may be made without consideration and approval by the committee. After the end of the study, the researchers must submit a final report to the committee containing a summary of the study's findings and conclusions.

Privacy and Confidentiality

24. Every precaution must be taken to protect the privacy of research subjects and the confidentiality of their personal information.

Informed Consent

- 25. Participation by individuals capable of giving informed consent as subjects in medical research must be voluntary. Although it may be appropriate to consult family members or community leaders, no individual capable of giving informed consent may be enrolled in a research study unless he or she freely agrees.
- 26. In medical research involving human subjects capable of giving informed consent, each potential subject must be adequately informed of the aims, methods, sources of funding, any possible conflicts of interest, institutional affiliations of the researcher, the anticipated benefits and potential risks of the study and the discomfort it may entail, post-study provisions and any other relevant aspects of the study. The potential subject must be informed of the right to refuse to participate in the study or to withdraw

CONFIDENTIAL Page 48 of 51

consent to participate at any time without reprisal. Special attention should be given to the specific information needs of individual potential subjects as well as to the methods used to deliver the information.

After ensuring that the potential subject has understood the information, the physician or another appropriately qualified individual must then seek the potential subject's freely-given informed consent, preferably in writing. If the consent cannot be expressed in writing, the non-written consent must be formally documented and witnessed.

All medical research subjects should be given the option of being informed about the general outcome and results of the study.

- 27. When seeking informed consent for participation in a research study the physician must be particularly cautious if the potential subject is in a dependent relationship with the physician or may consent under duress. In such situations the informed consent must be sought by an appropriately qualified individual who is completely independent of this relationship.
- 28. For a potential research subject who is incapable of giving informed consent, the physician must seek informed consent from the legally authorised representative. These individuals must not be included in a research study that has no likelihood of benefit for them unless it is intended to promote the health of the group represented by the potential subject, the research cannot instead be performed with persons capable of providing informed consent, and the research entails only minimal risk and minimal burden.
- 29. When a potential research subject who is deemed incapable of giving informed consent is able to give assent to decisions about participation in research, the physician must seek that assent in addition to the consent of the legally authorised representative. The potential subject's dissent should be respected.
- 30. Research involving subjects who are physically or mentally incapable of giving consent, for example, unconscious patients, may be done only if the physical or mental condition that prevents giving informed consent is a necessary characteristic of the research group. In such circumstances the physician must seek informed consent from the legally authorised representative. If no such representative is available and if the research cannot be delayed, the study may proceed without informed consent provided that the specific reasons for involving subjects with a condition that renders them unable to give informed consent have been stated in the research protocol and the study has been approved by a research ethics committee. Consent to remain in the research must be obtained as soon as possible from the subject or a legally authorised representative.

CONFIDENTIAL Page 49 of 51

- 31. The physician must fully inform the patient which aspects of their care are related to the research. The refusal of a patient to participate in a study or the patient's decision to withdraw from the study must never adversely affect the patient-physician relationship.
- 32. For medical research using identifiable human material or data, such as research on material or data contained in biobanks or similar repositories, physicians must seek informed consent for its collection, storage and/or reuse. There may be exceptional situations where consent would be impossible or impracticable to obtain for such research. In such situations the research may be done only after consideration and approval of a research ethics committee.

Use of Placebo

33. The benefits, risks, burdens and effectiveness of a new intervention must be tested against those of the best proven intervention(s), except in the following circumstances:

Where no proven intervention exists, the use of placebo, or no intervention, is acceptable; or

Where for compelling and scientifically sound methodological reasons the use of any intervention less effective than the best proven one, the use of placebo, or no intervention is necessary to determine the efficacy or safety of an intervention and the patients who receive any intervention less effective than the best proven one, placebo, or no intervention will not be subject to additional risks of serious or irreversible harm as a result of not receiving the best proven intervention.

Extreme care must be taken to avoid abuse of this option.

Post-Trial Provisions

34. In advance of a clinical trial, sponsors, researchers and host country governments should make provisions for post-trial access for all participants who still need an intervention identified as beneficial in the trial. This information must also be disclosed to participants during the informed consent process.

Research Registration and Publication and Dissemination of Results

- 35. Every research study involving human subjects must be registered in a publicly accessible database before recruitment of the first subject.
- 36. Researchers, authors, sponsors, editors and publishers all have ethical obligations with regard to the publication and dissemination of the results of research. Researchers have a duty to make publicly available the results of their research on human subjects and are accountable for the completeness and accuracy of their reports. All parties should adhere to accepted guidelines for ethical reporting. Negative and inconclusive as well as positive results must be published or otherwise made publicly available.

CONFIDENTIAL Page **50** of **51**

Sources of funding, institutional affiliations and conflicts of interest must be declared in the publication. Reports of research not in accordance with the principles of this Declaration should not be accepted for publication.

Unproven Interventions in Clinical Practice

37. In the treatment of an individual patient, where proven interventions do not exist or other known interventions have been ineffective, the physician, after seeking expert advice, with informed consent from the patient or a legally authorised representative, may use an unproven intervention if in the physician's judgement it offers hope of saving life, re-establishing health or alleviating suffering. This intervention should subsequently be made the object of research, designed to evaluate its safety and efficacy. In all cases, new information must be recorded and, where appropriate, made publicly available.

CONFIDENTIAL Page 51 of 51
